## 6. PARTICIPANT SAFETY

Participant safety will be monitored by study staff every 4 weeks through in person visits.

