Participants randomized to the intervention arm will have rapid access to ART at their first HIV visit, given that as of 2016, CD4 cell count no longer determines timing of ART initiation in Russia. Participants in this study will receive streamlined access to ART through a City AIDS Center infectionist who also sees patients at the City Addiction Hospital. The infectionist will facilitate initiation of ART medications either while the patient is still hospitalized at the City Addiction Hospital, or at their first visit to City AIDS Center following CAH discharge. CMs will work with study participants to arrange for the visit to the City AIDS Center (to initiate ART, if not initiated at CAH, or to get the second refill) and will be available to accompany participants to this visit. Once the initial HIV visit is made, participants will be able to receive follow up care and medication refills at their local HIV outpatient clinic.

Throughout the course of the study, participants will be expected to participate in three in-person assessments and blood draw visits (baseline, 6- [24 weeks], and 12 [52 weeks]-months). Intervention participants will receive 4 naltrexone implants while in the study. Ideally, implants will be inserted every 10-12 weeks starting at week 4 post-study enrollment (weeks 4, 16, 28, 40). Participants will be invited to come in every 4 weeks following implantation for medication visits. Ideally, medication visits will occur at weeks 4, 8, 12, 16, 20, 24, 28, 32, 36, 40, 44, 48, and 52. Full study assessments occur at weeks 24 and 52 (in addition to medication visit procedures). Implant visits 2, 3, and 4 will involve the collection of blood for laboratory testing to monitor liver toxicity.

In addition to the 240 RCT participants, we will also recruit providers and administrators from HIV and narcology care systems to participate in surveys and in-depth interviews at study launch and 12, and 24-months post-launch to explore their perspectives and experiences with care coordination between the narcology and HIV care systems. A subset of LINC-II participants will also be invited to participate in in-depth interviews to discuss their experiences with care coordination at baseline, 6- and 12-months post enrollment.

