### **3.5 MEDICATION CONSIDERATIONS**

#### **3.5.A SYMPTOM MONITORING**

The study staff (research clinicians [addiction physicians with extensive experience performing pharmacotherapy trials]) have extensive experience administering implantable and injectable naltrexone, and specimen collection via prior OUD pharmacotherapy studies. They will be trained to assess for adverse medication effects and will follow established protocols for identifying and monitoring any ongoing adverse events, including referral to treatment as appropriate. Study participants will be actively monitored for adverse events. Symptoms will be monitored every four weeks (and more frequently, if necessary) by trained clinical staff, while the participants are administered study medications.

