### **3.6 SCHEDULE OF DATA COLLECTION**

Intervention Group								
		Pre-screen	Screener and Baseline	Implant visits	Medication Checks (every 4 weeks post implant)	6-month visit (24 weeks)	12 month visit (52 weeks)	

			Screener	Baseline			
Screening	Verification of HIV, pregnancy, AST/ALT	X					
	Screening Questions		X				
Enrollment	Sign Informed Consent		X				
	Complete contact information/verify numbers			X			
	Randomization			X			
Laboratory	Clinical Values			X	X	X	X
	Pregnancy Test		X		X	X	X
	Urine Drug Test			X	X	X	X
	CD4			X		X	X
	HVL			X		X	X
	ALT/AST				X		
Assessment	Full Study Assessment			X		X	X
	Qualitative Assessment			X		X	X
	Medical Record Review	X				X	X
Intervention	Symptom Management/Adverse Events			X	X	X	X
	Naloxone challenge			X	X		
	Naltrexone Injection			X			
	Naltrexone Implant				X		
	Brief Counseling				X	X	X
Other	Compensate for Participation			X	X	X	X
	Provide Resource Card			X			
	Report Adverse Events			X	X	X	X
	Complete Tracking Forms			X	X	X	X

Control Group						
		Pre-screen	Screener and Baseline Visit		6 mo (24 weeks)	12 mo (52 weeks)
			Screener	Baseline		
Screening	Verification of HIV, pregnancy, AST/ALT	X				
	Screening Questions		X			
Enrollment	Sign Informed Consent		X			
	Complete contact information/verify numbers			X		
	Randomization			X		
Laboratory	Clinical Values			X	X	X
	Pregnancy Test		X			
	Urine drug Test				X	X
	CD4			X	X	X
	HVL			X	X	X
Assessment	Full Study Assessment			X	X	X
	Qualitative Assessment			X	X	X
	Medical Record Review	X			X	X
Other	Provide Resource Card			X		
	Compensate for Participation			X	X	X
	Complete Tracking Forms			X	X	X

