#### **Control Group:**

- During the **24-, and 52-week assessments**, the Pavlov RA will:
  - Review and update locator/contact information, verifying new numbers, as necessary
  - Send participant for phlebotomy (CD4, HVL), collect clinical data (weight, blood pressure)
  - Administer assessment questionnaire
  - Conduct urine drug test
  - Compensate participant and schedule next visit
  - **Subset of all participants:** In-depth interview

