## 6.2 THE METHODS AND TIME FOR ASSESSING, RECORDING, AND ANALYZING SAFETY PARAMETERS

- For participants randomized to the LINC-II intervention, symptoms will be assessed at baseline to document any chronic conditions or symptoms that existed prior to introduction of study medication. These will be documented on the Baseline AE log. This list will be reviewed and compared to reported events throughout the study. *If the participant reports the same ongoing symptom (same severity) during subsequent visits, the symptom should not be recorded as an Adverse Event (AE). If the event is new (not previously reported) or worsened, as determined by RA, then it will be considered an AE and recorded and reported as described below.*
- During each scheduled visit, the RA will ask the participant how he or she feels and review the previously reported symptoms. Any event that meets the above criteria for an AE/SAE/UP must be recorded. In the case of unresolved AEs, clinical staff will update the AE log with any follow-up information that is gathered during their investigation.
- The site will receive the results of all blood work that is performed on study participants from the designated lab. If the lab results meet the criteria described in the protocol as an AE and are considered clinically significant by the site clinician then an AE will be recorded.
  - Participants will be alerted of abnormal lab results and will receive a recommendation to see their local provider (please see section 3.3C for protocol specific to AST/ALT results). All abnormal lab results obtained at the baseline visit will be listed on the Baseline AE log. During follow-up visits, abnormal lab results will be listed as an AE only if the abnormal lab results meet one of the points below:
    - Develop at follow-up (i.e., were not previously recorded at baseline).
    - Worsen in severity compared to what was previously recorded at baseline.
    - Or are considered clinically significant.
  - All AEs will be assessed to determine if they meet criteria for a Serious Adverse Event (SAE). If the AE is serious, then the SAE form must be completed and appropriate reporting measures followed (see below). Investigators are encouraged to consult with the US team, if they are uncertain how to classify an event.
  - The list of participant's current medications will be reviewed and updated at every study visit, starting at baseline.

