### **Activities of Daily Living (ADL)**

\*Instrumental ADL refer to preparing meals, shopping for groceries or clothes, using the telephone, managing money, etc.

\*\*Self care ADL refer to bathing, dressing and undressing, feeding self, using the toilet, taking medications, and not bedridden.

- Assessment of expectedness (is the event anticipated in terms of nature, severity, or frequency) given (a) the research procedures that are described in the IRB protocol and informed consent document; and (b) the characteristics of the subject population being studied
- Assessment of relatedness to Naltrexone
- Any actions taken

Following the initial report, additional information may need to be gathered to complete the AE and SAE forms and to evaluate the event for relatedness. This process may include seeking hospital discharge reports, physician records, autopsy records or any other type of records or information necessary to provide a complete and clear picture of the SAE and events preceding and following the event.

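### Adverse-event collection is scheduled only in the intervention arm, so a between-arm comparison of AE/SAE records would carry ascertainment bias

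*Combined protocol and SAP*

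**What the plan says.** Section 6 opens with an unqualified statement: "Participant safety will be monitored by study staff every 4 weeks through in person visits". Section 3.5.A is narrower and ties the same frequency to treatment: "Symptoms will be monitored every four weeks (and more frequently, if necessary) by trained clinical staff, while the participants are administered study medications". The visits that would carry this monitoring are the intervention arm's medication visits in section 3.1: "Ideally, medication visits will occur at weeks 4, 8, 12, 16, 20, 24, 28, 32, 36, 40, 44, 48, and 52".

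Section 3.6 gives one schedule per arm. The intervention schedule has the rows "Symptom Management/Adverse Events" and "Report Adverse Events". The control schedule has neither. The control visit flow in section 4.4, for weeks 24 and 52, covers contact details, phlebotomy and clinical data, the questionnaire, the drug test ("Conduct urine drug test"), compensation and, for a subset, an interview. No task concerns adverse events.

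Section 6.2 is mixed. Its first bullet sets up the baseline record of symptoms for one arm: "For participants randomized to the LINC-II intervention, symptoms will be assessed at baseline". The bullets that follow name no arm. They have the assessor ask about symptoms at each scheduled visit and require qualifying events to be recorded, including those learned of between visits. Section 7.4 lists the AE/SAE form as completed when needed, again with no arm named. The only causality item listed in section 6.3.B is "Assessment of relatedness to Naltrexone".

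Section 8 plans no comparison of safety between arms.

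**The concern.** Section 6.1 defines an adverse event without regard to relatedness and counts death and hospitalisation as serious, so events in controls qualify. Section 3.3.C warns that overriding the opioid blockade may be fatal and that sensitivity to opioids may rise after naltrexone. Such events also occur in this population without naltrexone. The randomised control arm is the trial's means of telling the two apart, and it works only if events are sought in the same way in both arms.

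If staff work from the schedules, one arm is asked about events about every four weeks against a baseline list of symptoms. The other is seen twice with no instruction to ask. More recorded events in the intervention arm could then reflect more asking, and a real reduction could be hidden. Section 6.3.C also requires a periodic statement to the US review board about the pattern of adverse events in total. That statement is hard to support when the two halves of the trial are collected differently.

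**Working it through.** The plan gives no figure to reproduce here. The check is a count of contacts, a side-by-side reading of the text, and an illustration on assumed values.

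**Contacts.** Monitoring every 4 weeks over 52 weeks implies 52 / 4 = 13 contacts.

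| Item | Intervention | Control | Source |
|---|---|---|---|
| Scheduled follow-up contacts | 13 | 2 | 3.1, 3.6, 4.4 |
| Adverse-event rows in schedule | 2 | 0 | 3.6 |
| Adverse-event or symptom task in visit flow | symptom monitoring at each medication visit | none | 4.4 |
| Baseline symptom log | yes | not described | 6.2 |
| Asked about symptoms at each scheduled visit | yes | yes, if 6.2 is read literally | 6.2 |
| Duty to record any event | yes | yes, if 6.2 is read literally | 6.2 |

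The intervention arm matches the section 6 statement exactly (13 of 13). The control arm has 2, a ratio of 13 / 2 = 6.5. Suture-removal visits are not counted, because the schedule has no column for them.

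**Sources common to both arms.** The full assessment is scheduled in both arms at 6 and 12 months (3.6). Per the table in 5.2 it includes the overdose and suicide items and health care utilisation. Medical records are reviewed in both arms, including for withdrawn participants who do not refuse (3.7.D). These sources have limits:
- The item content is not shown, so it is unknown whether inpatient stays are asked about.
- Chart review is described as covering HIV and addiction care.
- A questionnaire cannot be answered by someone who has died or been lost. Section 2.8.A assumes 20% loss for the primary outcome, 240 × 0.20 = 48 people. The same loss on the questionnaire would leave 192 respondents.
- Section 2.8.A expects some deaths, but no systematic way of finding them is described.

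**Illustration of the bias.** The documents give no serious-event rate and no capture rate, so all inputs except the arm size (120, section 2.4) are assumptions. Let the true proportion p be equal in both arms, with full capture in the intervention arm and capture c in controls.

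Apparent risk ratio = p / (c × p) = 1 / c.

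Chance of a significant apparent excess (two-sided 5%, n = 120 per arm) = Φ{ [d − 1.96 √(2m(1−m)/n)] / √([p(1−p) + cp(1−cp)]/n) }, with d = p − cp and m = (p + cp)/2.

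For p = 10% and c = 50%: d = 0.05 and m = 0.075. The null term is 1.96 × √(2 × 0.075 × 0.925 / 120) = 0.0667. The denominator is √((0.09 + 0.0475) / 120) = 0.0339. Then (0.05 − 0.0667) / 0.0339 ≈ −0.49, and Φ = 0.31.

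| Control capture c | Apparent risk ratio | p = 10% | p = 20% | p = 30% |
|---|---|---|---|---|
| 80% | 1.25 | 8% | 12% | 18% |
| 60% | 1.67 | 21% | 39% | 59% |
| 50% | 2.0 | 31% | 58% | 80% |

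With equal capture, a spurious excess in that direction would be expected about 2.5% of the time.

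**The case against.** The case on the other side has real force. The operative rules in section 6.2 are not limited to one arm. Controls have scheduled visits, so read literally the assessor asks them about symptoms at weeks 24 and 52 and records what qualifies. Section 3.5.A already links the four-weekly frequency to study medication, so the section 6 sentence may be no more than a loose introduction. Checking more often in the arm that receives naltrexone is a reasonable monitoring choice. No safety outcome or between-arm safety test is planned, so no stated objective is broken.

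A reader might infer that deaths, hospitalisations and overdoses cannot be compared between arms at all, or that controls have no elicitation of events. The documents do not support either reading. Overdose and health care use are asked in both arms at the same two time points, charts are reviewed in both arms, and section 6.2 can be read to cover controls.

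What remains is the conflict itself. Section 6.2 judges an event as new or worsened against a baseline list whose symptom entries are described only for intervention participants. Site staff working from the control schedule and visit flow find no prompt to ask. Arm-neutral wording in one section does not guarantee equal capture when the schedules for the two arms differ.

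**Conclusion.** The point holds as an inconsistency with a consequence. AE/SAE assessment and reporting are scheduled in the intervention arm only, with 13 contacts against 2. This conflicts with the unqualified sentence in section 6 and with the arm-neutral rules in section 6.2. Any comparison of AE/SAE records between arms would be open to ascertainment bias.

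The size of that bias cannot be derived from the documents. The risk ratios of 1.25 to 2.0 rest on assumed control capture of 50% to 80%, complete capture in the intervention arm and equal true risk. If staff apply section 6.2 fully at both control visits, the gap is smaller.

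Overdose can be compared from the questionnaire, within the limits of self-report and loss to follow-up. Deaths and hospitalisations are weaker, because no systematic capture in controls is described. The primary outcome is not affected. The point should also not be stretched to liver injury: section 3.7.B measures AST and ALT during follow-up in the intervention arm only, by stated plan, and the change below would not alter that.

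**What to change.** 1. Add an AE/SAE row, covering at least deaths, hospitalisations and overdoses, to the control schedule in section 3.6 and the control visit flow in section 4.4 at weeks 24 and 52. Use the same form as the intervention arm, together with the chart review already planned.
2. State in section 8 that serious events will be reported by arm using only sources common to both arms: the 6- and 12-month visits and chart review. List events found only at medication visits separately for the intervention arm.
3. Reconcile sections 3.5.A, 3.6, 4.4, 6 and 6.2, so that section 6 says which arm the four-weekly contacts apply to and section 6.2 says what is done for controls, including at baseline.

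The cost is a few minutes and some adverse-event paperwork at two visits that already take place. No extra visit or procedure is needed. Setting aside events found only at medication visits makes the between-arm comparison less complete, but it puts both arms on the same footing.

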### 6.1. SPECIFICATION OF SAFETY PARAMETERS

An **Adverse Event (AE)** is defined as any untoward or unfavorable medical occurrence in a human subject, including any abnormal sign (for example, abnormal physical exam or laboratory finding), symptom, or disease, temporally associated with the subject's participation in the research, whether or not considered related to the subject's participation in the research.

An AE can therefore be any new sign, reaction, symptom, event, disease or a worsening in frequency or severity of a preexisting condition that occurs during the course of the study.

*Stable chronic conditions that were present prior to study entry and do not worsen are not considered AEs.*

**SERIOUS Adverse Event (SAE)** – is any adverse event that

- (1) results in death;
- (2) is life-threatening;
- (3) results in inpatient hospitalization or prolongation of existing hospitalization;
- (4) results in a persistent or significant disability/incapacity;
- (5) results in a congenital anomaly/birth defect; or
- (6) based upon appropriate medical judgment, may jeopardize the subject's health and may require medical or surgical intervention to prevent one of the other outcomes listed in this definition (examples of such events include allergic bronchospasm requiring intensive treatment in the emergency room or at home, blood dyscrasias or convulsions that do not result in inpatient hospitalization, or the development of drug dependency or drug abuse).

Life-threatening means that the event places the subject at immediate risk of death from the event as it occurred.

**Unanticipated Problem (UP)** – is defined as an event, experience or outcome that meets all three of the following criteria:

- is unexpected; AND
- is related or possibly related to participation in the research; AND
- suggests that the research places subjects or others at a greater risk of harm (including physical, psychological, economic, or social harm) than was previously known or recognized.

Possibly related means there is a reasonable possibility that the incident, experience, or outcome may have been caused by the procedures involved in the research

Unexpected means the nature, severity, or frequency of the event is not consistent with either:

- the known or foreseeable risk of adverse events associated with the procedures involved in the research that are described in (a) the protocol-related documents, such as the IRB-approved research protocol, any applicable investigator brochure, and the current IRB-approved informed consent document, and (b) other relevant sources of information, such as product labeling and package inserts; or
- the expected natural progression of any underlying disease, disorder, or condition of the subject(s) experiencing the adverse event and the subject's predisposing risk factor profile for the adverse event.

**Suspected Adverse Drug Reaction** – Any adverse event for which there is a reasonable possibility that the drug caused the adverse event. Reasonable possibility means there is evidence to suspect a causal relationship. It is considered unexpected if it is not consistent with the risk information described in the general investigational plan. A suspected adverse drug reaction will be defined as a recorded adverse event that is unexpected and deemed to be possibly, probably, or definitely related to the study drug.

## 6.2 THE METHODS AND TIME FOR ASSESSING, RECORDING, AND ANALYZING SAFETY PARAMETERS

- For participants randomized to the LINC-II intervention, symptoms will be assessed at baseline to document any chronic conditions or symptoms that existed prior to introduction of study medication. These will be documented on the Baseline AE log. This list will be reviewed and compared to reported events throughout the study. *If the participant reports the same ongoing symptom (same severity) during subsequent visits, the symptom should not be recorded as an Adverse Event (AE). If the event is new (not previously reported) or worsened, as determined by RA, then it will be considered an AE and recorded and reported as described below.*
- During each scheduled visit, the RA will ask the participant how he or she feels and review the previously reported symptoms. Any event that meets the above criteria for an AE/SAE/UP must be recorded. In the case of unresolved AEs, clinical staff will update the AE log with any follow-up information that is gathered during their investigation.
- The site will receive the results of all blood work that is performed on study participants from the designated lab. If the lab results meet the criteria described in the protocol as an AE and are considered clinically significant by the site clinician then an AE will be recorded.
  - Participants will be alerted of abnormal lab results and will receive a recommendation to see their local provider (please see section 3.3C for protocol specific to AST/ALT results). All abnormal lab results obtained at the baseline visit will be listed on the Baseline AE log. During follow-up visits, abnormal lab results will be listed as an AE only if the abnormal lab results meet one of the points below:
    - Develop at follow-up (i.e., were not previously recorded at baseline).
    - Worsen in severity compared to what was previously recorded at baseline.
    - Or are considered clinically significant.
  - All AEs will be assessed to determine if they meet criteria for a Serious Adverse Event (SAE). If the AE is serious, then the SAE form must be completed and appropriate reporting measures followed (see below). Investigators are encouraged to consult with the US team, if they are uncertain how to classify an event.
  - The list of participant's current medications will be reviewed and updated at every study visit, starting at baseline.

- If an event is discovered outside of the scheduled study visits, it must still be recorded accordingly.
- Action Taken will be determined by the RAs for all AEs that are Mild and Moderate and by Drs. [name] or [name] for SAEs and AEs that are severe, life-threatening or fatal.

